## **4.2 Endpoints**

### **4.2.1 Primary endpoints**

Comparison of the proportion of pregnancies in pregnant women who have completed 22 weeks of pregnancy and treated with Levemir® to pregnant women who have completed 22 weeks of pregnancy and treated with other basal insulin regimens resulting in none of the following events:

- Major congenital malformations
- Perinatal death
- Neonatal death

Assessed at up to 4 weeks after delivery.

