#### 4.2.2.3 Infant endpoints assessed at 1 year of age

- Height at the age of 1 year
- Weight at the age of 1 year
- Proportion with DM
- Proportion with changes (progression/regression) of major congenital malformations

For pregnancies with multiple foetuses each foetus will be counted individually for the primary endpoint, the other pregnancy outcome endpoints, and the infant endpoints at 1 year of age.

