## 6.2 Inclusion criteria

For an eligible patient, all inclusion criteria must be answered “yes”.

1. Informed consent obtained before any data collection
2. Woman with a positive pregnancy test
3. Diabetes mellitus type 1 or 2, diagnosed prior to conception
4. Currently treated with Levemir® or other injectable antidiabetic treatment(s)
5. Unchanged basal insulin or other injectable antidiabetic treatment product (for those not treated with basal insulin) 4 weeks prior to and following conception

An eligible woman may be included in the Diabetes Pregnancy Registry more than once, should the pregnancies occur within the recruitment period.

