## 8 Methods and assessments

The Diabetes Pregnancy Registry will include maternal and paediatric assessments as per standard practise. There are differences in the endpoints covering the gestation period, the delivery, the pregnancy outcomes, the postpartum visit and the follow-up in the infants. The variables on the study forms will depend on these different endpoints.

All parameters which will be collected in this registry are defined in accordance with normal clinical practice. Relevant registry forms for the baseline visit including potential confounders, standard routine visits, delivery visit, the postpartum visit and the follow-up of the infants are developed together with some of the study sites participating in the registry.

Signed informed consent must be obtained prior to any data entry into the registry.

After the Informed Consent Form has been signed, patients will be allocated an ID number, which will remain unchanged throughout the study. The physician will assign each enrolled patient with a unique 6 digit patient number. The patient number is composed of 3 digits unique for each study site followed by 3 consecutive digits for each enrolled patient on the study site. If an eligible woman is included in the Diabetes Pregnancy Registry more than once, she will be allocated a new patient ID number for each pregnancy that may occur during the recruitment period. The infant(s) of the patient will be allocated the same ID number as its mother followed by a "Xn" at the end of the 6 digit patient number (n=1, 2, 3 and so forth for each child).

Patients enrolled in the study will be provided with contact address and telephone number of the physician site and/or staff.

In case a patient is withdrawn from the study the physician will ensure that the primary reason for discontinuation will be specified in the eCRF.

This section describes the general study procedures applicable for all patients. Visit and contact specific procedures are described in sub-sections below.

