### **8.1.1 Baseline visit**

Signed informed consent must be obtained before any data recording is performed for the purpose of this non-interventional study.

The following will be performed at the baseline visit which will occur as soon as the woman has discovered her pregnancy through a positive pregnancy test:

- Check of eligibility against inclusion criteria (section [6.2](#))
- Check whether the patient has previously participated in the registry (if yes, please state previous patient ID number)
- Demographics (section [8.3.1](#))
- Obstetric history (section [8.3.2](#))
- Maternal medical history (section [8.3.3](#))
- Maternal diabetes history (section [8.3.3](#))
- Current insulin and/or injectable antidiabetic treatment and/or OAD use (section [8.3.3](#))
- Concomitant illnesses (section [8.3.4](#))
- Concomitant medication (section [8.3.4](#))
- Anthropometric measurements (section [8.3.5](#))
- Vital signs (section [8.3.6](#))
- Current pregnancy (section [8.3.7](#))
- HbA1c level assessed according to standard routine at local laboratories (HbA1c level measured  $\leq$  16 weeks prior to baseline visit is acceptable as baseline visit data)

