#### 14.4 Statistical methods

All endpoints will be analysed on the analysis set.

Continuous variables (maternal HbA1c at start of pregnancy, at the end of each trimester, and height and weight of the infant at 1 year) will be summarised with descriptive statistics (number of observations with available values, number of observations with missing values, mean, 95% confidence interval of the mean, standard deviation, minimum, median, maximum), and categorical variables and Apgar score will be displayed in frequency tables (N, %). The mean of the Apgar score will also be computed.

The primary endpoint, proportion of pregnancies resulting in the combined pregnancy outcome will be computed for the Levemir® group, and for the other basal insulin group, the difference between these proportions will be computed along with the 95% confidence interval and the p-value using Fisher's exact test. This simple analysis might be biased if type of basal insulin is confounded with other risk factors for a negative birth outcome, so to take this into account the primary endpoint will also be analysed using logistic regression, see the description below.

This analysis will be performed for all other endpoints which are proportions, both maternal endpoints, pregnancy outcome endpoints, and infants' endpoints at 1 year of age.

In addition, the primary endpoint will be analysed using logistic regression. Both crude and adjusted models will be performed. The model will include treatment group (Levemir®/other basal insulins group), and adjust for potential confounders such as study site, type of DM, race, hypertension, major hypoglycaemic events during pregnancy, folic acid intake, and use of GLP-1 agonists during pregnancy. Furthermore, HbA1c at start of pregnancy, end of first trimester, and end of second trimester, age and BMI of the woman at baseline, duration of DM, blood pressure and previous foetal pregnancy complications will be adjusted for as appropriate. Adjustments will be performed in a stepwise manner, and further specified in the Statistical Analysis Plan. Similar analyses will be performed for all other endpoints which are proportions for maternal endpoints, or proportions for pregnancy outcome endpoints.

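### Foetuses and repeat pregnancies of the same woman are analysed as independent units, so the model-based standard errors and confidence intervals come out slightly too narrow where related units share a treatment group

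*Protocol*

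**What the plan says.** Protocol section 4.2.1 words the primary endpoint per pregnancy: "Comparison of the proportion of pregnancies in pregnant women who have completed 22 weeks of pregnancy". Section 13 defines the analysis set as pregnancies. The sample size counts pregnancies in sections 6.1 and 14.2, and subjects in 14.3.

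The counting rule at the end of section 4.2.2.3, also given in the Summary, differs: "For pregnancies with multiple foetuses each foetus will be counted individually for the primary endpoint". It extends to the other pregnancy outcome endpoints and to the infant endpoints at 1 year.

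Repeat entry is allowed in section 6.2: "An eligible woman may be included in the Diabetes Pregnancy Registry more than once, should the pregnancies occur within the recruitment period". Under section 8 "she will be allocated a new patient ID number for each pregnancy that may occur during the recruitment period". The link is not lost, because section 8.1.1 asks sites to "Check whether the patient has previously participated in the registry (if yes, please state previous patient ID number"), and section 8 builds each infant's number from the mother's.

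For the primary endpoint, section 14.4 says that "the difference between these proportions will be computed along with the 95% confidence interval and the p-value using Fisher's exact test". The same analysis applies to the other endpoints that are proportions. Crude and adjusted logistic regression follow, and ANCOVA for the continuous endpoints. The section refers only the stepwise covariate adjustment to the SAP. Nowhere does the protocol mention a cluster term, a random effect, GEE, a robust variance or an analysis with one record per woman.

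**The concern.** Twins share a mother, an exposure and, almost always, a time of delivery. A woman's successive pregnancies share her diabetes and her obstetric risk; the protocol accepts this when it adjusts for previous foetal complications. Their outcomes are therefore likely to be positively correlated, and the named methods, as written, count each as a separate piece of information.

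At stake is the stated precision of a post-authorisation safety comparison with few events, where an interval that is too narrow can suggest either reassurance or a signal that the data do not support. The unit is also inconsistent: a proportion of pregnancies and a proportion of foetuses have different denominators, and the sample size was set for the first.

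**Working it through.** **1. The plan's own figure.** Inputs from sections 14.2 and 14.3: 611 per group, event-free proportion 93.5%, difference 3.5 points, two-sided 5%, 80% power. Exact power of Fisher's test for 93.5% against 97.0% is 79.9%, which matches. The pooled normal formula gives a total of 1158 without and 1270 with continuity correction, so the Fisher calculation is the one that fits. The enrolment figure also reproduces: 1222 / (1 − 0.40) = 2037. The 1222 is thus a calculation for independent units, with no design effect.

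**2. Design effect, pairs within one group.** Let a share s of counted units lie in pairs with correlation ρ. Each such unit adds one covariance term, so

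Var = p(1 − p)/n × (1 + sρ), DE = 1 + sρ, and the standard error is multiplied by √DE.

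The protocol gives neither s nor ρ, so the values below are assumptions. The last two columns give the real size of a nominal 5% Wald test, 2 × [1 − Φ(1.96/√DE)], and 1222 × DE rounded up.

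| s | ρ | DE | SE multiplier | Wald size | Total N |
|---|---|---|---|---|---|
| 5% | 0.3 | 1.015 | 1.007 | 5.2% | 1241 |
| 6% | 0.5 | 1.030 | 1.015 | 5.35% | 1259 |
| 10% | 0.5 | 1.050 | 1.025 | 5.6% | 1284 |
| 20% | 0.5 | 1.100 | 1.049 | 6.2% | 1345 |

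Over s = 5% to 20% and ρ = 0.3 to 0.5, the correct standard error is 0.7% to 4.9% larger than the one computed.

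**3. Pre-term delivery.** Twins delivered together have the same outcome, so ρ is about 1 and DE is about 1 + s. If 4% of counted foetuses were twins, DE = 1.04 and the multiplier is √1.04 = 1.020. At ρ = 0.3 the same twins would give √1.012 = 1.006.

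**4. Pairs split across groups.** Only repeat pregnancies can be split. With n per group and m split pairs, s = m/n, the covariance is subtracted:

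Var(difference) = 2p(1 − p)/n × (1 − sρ).

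Ignoring the correlation then makes the standard error too large.

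**5. Real type I error on the primary endpoint.** Simulation with 100,000 runs, 611 per group, all pairs within a group, at event rates of 2.7% (the 97.3% event-free proportion observed, section 14.3) and 6.5%:

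| Test | Independent units | s = 6%, ρ = 0.5 | s = 20%, ρ = 0.5 |
|---|---|---|---|
| Fisher | 3.4% and 3.8% | 3.6% and 4.1% | 4.4% and 4.9% |
| Uncorrected chi-square | 4.9% and 4.9% | 5.3% and 5.3% | 6.3% and 6.1% |

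The chi-square test stands in for the Wald test of the crude logistic model. Fisher's test starts well below 5%, and the clustering uses up that slack without exceeding it. The chi-square test has no slack.

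**The case against.** **The headline test is safe.** A reader might infer that the primary p-value is too optimistic. The simulation does not bear this out: Fisher's test stayed below 5% throughout, and replacing it with a model-based test would move its size up towards 5%. This stands, and Fisher's test need not be dropped.

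**The SAP may deal with it.** The protocol says logistic regression without naming a variance estimator, and it names no interval method for the difference. A robust variance is a detail that an SAP could supply, and the linking ID is collected. This stands in part: the model-based statement holds for the methods as the protocol words them. The counting rule, the per-pregnancy wording and Fisher's test are fixed in the protocol itself, which defers only the stepwise adjustment.

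**The effect is small.** To count twice in the primary analysis by repeat entry, a woman must enrol by week 16 both times, complete 22 weeks both times and keep her basal insulin each time. The adjusted models also include maternal factors that may absorb some of the correlation. Both arguments stand, and the upper end of the assumed range may well not be reached.

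**One twin pregnancy could decide the result.** A reader might infer this from the low event count. At 97.3% event-free there are 1222 × 0.027 = 33 events, and a double death is 2/33 = 6% of them. At the planning values there are 611 × 0.065 + 611 × 0.03 = 58 events, and the share is 2/58 = 3.4%. Merging such a pair into one record also removes a record from the denominator: Fisher's p is 0.047 for 10/611 against 22/611 and still 0.047 for 10/611 against 21/610. It rises to 0.067 only if the event is removed and the record kept.

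**The unit is stated.** The counting rule is explicit, so the intention can be read. Its conflict with the endpoint wording, the analysis set and the sample size remains.

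**Conclusion.** The point holds as a modest one. The protocol sets up related units, analyses them as independent, and uses one unit in the endpoint and sample size and another in the counting rule. Where related units share a treatment group, standard errors in the logistic and ANCOVA models and the intervals for differences are understated by roughly 1% to 5%. This rests on the assumed 5% to 20% in pairs and correlation 0.3 to 0.5. For pre-term delivery the effect per twin pair is larger.

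A reader might infer that standard errors are understated for every endpoint. The documents do not support that. The foetus rule does not cover the maternal endpoints, so only repeat entry affects them, and repeat pregnancies split across groups push the other way. The result for Fisher's test applies to the primary endpoint at the event rates and pair shares simulated; it was not checked for pre-term delivery.

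**What to change.** In Protocol section 4.2, state one unit of analysis for each family of endpoints, and use the same unit in section 14. In section 14.4:

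- Fit the logistic and continuous models with GEE or cluster-robust standard errors, with the woman as cluster. Link repeat entries through the previous patient ID and infants through the mother's number.
- Take the risk difference and its 95% confidence interval from that approach.
- Keep Fisher's p-value, if wanted, as the simple unadjusted analysis, labelled as ignoring clustering.
- Add a sensitivity analysis with one record per woman: her first pregnancy, counted as an event if any foetus has one.

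The cost is a wording change in the protocol and SAP, a little more analysis work and slightly wider intervals. No new data are needed.

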## 5 Study design

### 5.1 Type of study

This study is a post-authorisation commitment to the European Medicines Agency – a Post Authorisation Safety Study (PASS) - to monitor the long-term safety of Levemir® in pregnant women to cover the gestation and lactation. This international, prospective, non-interventional, multi-centre cohort study will monitor and assess the safety of Levemir® use during pregnancy as well as monitoring the health status of the infants at 1 month and at 1 year of age. The same parameters will also be monitored and assessed for other injectable antidiabetic treatment regimens.

The study is non-interventional as the assignment of the patient to a particular therapeutic strategy is not decided in advance by a trial protocol but falls within current practice and the prescription of the medicine is clearly separated from the decision to include the patient in the study.

Enrolment of women on injectable antidiabetic treatment regimens will most likely also include women treated with injectable antidiabetic drugs apart from insulins. Treatment with such injectable antidiabetic drugs for example GLP-1 agonists during pregnancy is off-label use. Due to the non-interventional study design of the Diabetes Pregnancy Registry women treated with injectable antidiabetic drugs other than insulins will be included either if they are treated with other injectable antidiabetic drugs solely or treated with a combination of insulin and other injectable antidiabetic drugs. The information on all insulins and other injectable antidiabetic treatment regimens is collected for the completeness of the non-interventional real-world data collection in order to obtain a comprehensive overview of the treatment patterns used in pregnant women with DM.

Change in dosage, dose interval and add-on or removal of bolus insulin, oral antidiabetic drugs and/or GLP-1 agonists is expected and will not exclude pregnant women to participate in the registry and in the primary and secondary endpoint analysis. A change in type or brand of basal insulin after baseline visit will lead to exclusion from the primary and secondary endpoint analysis, but not from the registry itself.

The study period includes the gestation periods of the pregnant women and the follow-up of the infants at 1 month and at 1 year of age.

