### **STUDY POPULATION:**

Women with DM, who are pregnant and treated with Levemir® or other injectable antidiabetic treatment regimens, and who have not changed basal insulin or other injectable antidiabetic treatment product (for those not treated with basal insulin) 4 weeks prior to and following conception will be included in the Diabetes Pregnancy Registry.

For the statistical analyses only women treated with basal insulin will be included. The group of women treated with Levemir® will be compared to the group of women treated with other basal insulins.

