### 6.1 Number of patients to be studied

Estimated number of patients to be included during the recruitment period: minimum: 2,037

Recruitment will close once it is secured that 611 patients treated with Levemir® are eligible for the primary analysis.

Based on sample size calculations (Section 14) the number of pregnancies needed for the primary endpoint calculations is 1,222 pregnancies with information on the primary endpoint pregnancy outcomes:

- perinatal death
- neonatal death
- liveborn infant with 1 month follow up (irrespective if there is a malformation or not)

Liveborn infants will be followed up until 1 year with the aim of collecting data for the secondary endpoints.

It is expected that approximately 60% of the included pregnancies will be fulfilling the criteria for primary endpoint calculations, as 40 % are assumed to be excluded or used for secondary endpoints. These 40% of subjects are assumed to consist of subjects who experience one or more of the following: abortion (spontaneous or induced), change in basal insulin treatment, treatment with other antidiabetic treatment regimens, or lost to follow-up.

Therefore, it is calculated that a minimum of  $(1,222/60*100)$  2,037 patients are to be included in the study.

Note that the study plans to include a minimum of 2,037 patients treated with injectable antidiabetic treatment regimens, but that only women treated with Levemir® and other basal insulins will be included in the primary analyses.

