## 6.5 Rationale for study population

The Diabetes Pregnancy Registry is a non-interventional epidemiological study where data are collected on standard routine procedures. The results and observations from the registry will, hence, be more broadly applicable to the real-world population of pregnant women with DM, and their infants than study populations enrolled in a typical randomised controlled trial.

Only women with either T1DM or T2DM who are treated with Levemir® or other injectable antidiabetic treatment regimens and who have not changed basal insulin or other injectable antidiabetic product (for those not treated with insulin) 4 weeks prior to and following conception will be included. During the pregnancy the women attend regular visits to specialist clinics for the treatment of their DM and therefore, it is optimal to contact experienced clinics with a high number of potential candidates.

Gestational DM has been excluded because the women may not develop the disease until late in pregnancy, where the organogenesis is finalized and thereby the risk of malformation significantly reduced. Furthermore, at least a fraction of these may control the gestational DM by diet alone.

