### **13 Evaluation of patients for analysis**

The analysis set will consist of the pregnancies among patients who are treated with basal insulin and have not changed basal insulin product 4 weeks prior to conception and during pregnancy.

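### The only analysis set drops every woman who changes basal insulin during pregnancy, so all group comparisons are conditioned on an event after exposure

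*Protocol*

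**What the plan says.** Section 5.1 sets the rule: "A change in type or brand of basal insulin after baseline visit will lead to exclusion from the primary and secondary endpoint analysis". The women stay in the registry. The sentence before it lists changes that do not exclude: "Change in dosage, dose interval and add-on or removal of bolus insulin, oral antidiabetic drugs and/or GLP-1 agonists is expected".

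Section 13 defines the analysis set as pregnancies in women on basal insulin who "have not changed basal insulin product 4 weeks prior to conception and during pregnancy". The Summary (Section 1) and Section 4.1 limit the primary and secondary comparisons to such women. Section 14.4 then says: "All endpoints will be analysed on the analysis set". The protocol names no other set.

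The contrast is one product against a pool. In Section 1, Study population, the Levemir group "will be compared to the group of women treated with other basal insulins".

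Section 6.1 expects that "approximately 60% of the included pregnancies will be fulfilling the criteria for primary endpoint calculations". It attributes the other 40% to "abortion (spontaneous or induced), change in basal insulin treatment, treatment with other antidiabetic treatment regimens, or lost to follow-up", without splitting that share by reason or by group.

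**The concern.** Whether a woman changes basal insulin is known only after exposure has begun and she has entered the cohort. Section 3.1 ties treatment adjustment in pregnancy to achieving glycaemic control without inducing hypoglycaemia, so a basal switch may be related to the outcomes under study. If it is, and if switching differs between groups, comparing only non-switchers can create or hide a difference. The logistic models in Section 14.4 adjust for covariates among the women who remain; they cannot bring back those removed. The limitations in Section 5.4 cover heterogeneity, confounding and incomplete registration, but not this selection.

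Two features of the rule add to this. First, a Levemir woman is caught only if she leaves Levemir, whereas a comparator woman is also caught when she moves to another non-Levemir basal insulin and stays in the same comparison group. Second, a longer pregnancy leaves more time to switch and so to be excluded. This matters for spontaneous abortion and pre-term delivery, where the length of pregnancy is part of the outcome.

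The boundary of the rule also differs between sections. Section 5.1 counts changes from the baseline visit on, while Section 13 covers the whole pregnancy. Baseline may be as late as 16 weeks, and inclusion criterion 5 guarantees an unchanged product only to 4 weeks after conception. A change between those two points is excluded by Section 13 and not addressed by Section 5.1.

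**Working it through.** **The plan's own figures.** Section 14.3 needs 611 + 611 = 1,222 analysable pregnancies, and 1,222 / (1 − 0.40) = 2,037 enrolled; this reproduces. Two-sided Fisher power by full enumeration, 611 per group, 93.5% versus 97.0% event-free, is 79.9%, in line with the plan. The 611 per group is counted after exclusions, so the sample size is not affected by this point.

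**Size of the possible distortion.** Inputs from the protocol:
- event rates of 2.7% (97.3% event-free observed, Section 14.3), 6.5% (the 93.5% threshold, Section 14.3) and 8.2% (Section 14.2);
- 611 per group; two-sided 5% level.

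Assumed, because the protocol gives none of these:
- the share s who switch in each group;
- the ratio r of event risk in switchers to that in non-switchers, the same in both groups;
- that each event rate applies to all women in both groups, switchers included, so there is no true difference.

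All-women risk p is the average of the two kinds of women: p = (1 − s)q + s·r·q, where q is the risk in non-switchers. Hence q = p / (1 + s(r − 1)), and q is what the planned set estimates.

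Example: p = 2.7%, r = 2, s = 5% (Levemir) and 15% (other). Levemir: 2.7 / 1.05 = 2.57%. Other: 2.7 / 1.15 = 2.35%. Spurious difference: 0.22 points.

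| p | s Levemir / other | r | q Levemir | q other | Spurious difference (points) | Rejection rate |
|---|---|---|---|---|---|---|
| 2.7% | 10% / 10% | 3 | 2.25% | 2.25% | 0 | 5.0% |
| 2.7% | 5% / 15% | 2 | 2.57% | 2.35% | 0.22 | 5.7% |
| 2.7% | 10% / 30% | 3 | 2.25% | 1.69% | 0.56 | 10.9% |
| 2.7% | 20% / 10% | 3 | 1.93% | 2.25% | −0.32 | 6.8% |
| 6.5% | 5% / 15% | 2 | 6.19% | 5.65% | 0.54 | 6.8% |
| 6.5% | 10% / 30% | 3 | 5.42% | 4.06% | 1.35 | 20.0% |
| 8.2% | 5% / 15% | 2 | 7.81% | 7.13% | 0.68 | 7.4% |
| 8.2% | 10% / 30% | 3 | 6.83% | 5.13% | 1.71 | 24.2% |

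Rejection rates use a large-sample two-sided test; Fisher's exact test, being conservative, would give somewhat lower values. With r = 1 the difference is zero whatever the shares.

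**A commoner maternal endpoint (all inputs assumed).** Hypoglycaemia risk 20% in non-switchers and 40% in switchers; 10% and 20% switch. All women: 0.9 × 20 + 0.1 × 40 = 22%, and 0.8 × 20 + 0.2 × 40 = 24%. The planned set shows 20% against 20%, and 2 points are lost.

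**What keeping switchers does to numbers.** If a fraction s of all enrolled women (assumed) is excluded for switching alone, the 2,037 enrolled yield 2,037 × (0.60 + s) pregnancies: 1,324 at 5%, 1,426 at 10%, 1,528 at 15% and 1,630 at 20%, against 1,222.

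**The case against.** The comparison under unchanged exposure is an open design choice, stated in the objectives, and keeping switchers mixes exposures. That stands as a reason to keep the non-switcher analysis, but not to have it alone in a safety study.

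Sensitivity sets often sit in the SAP, which is not at hand, and Section 14.4 allows further exploratory analyses. So it cannot be said that no planned analysis would reveal the problem. What can be said is that the protocol's objectives confine the comparisons to non-switchers. That is a stated rule, not a detail left open.

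Section 14.4 also promises to account for gestational age at entry and exact follow-up time where relevant. That can help among women in the set; it does not restore those removed.

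A reader might infer more than the protocol supports:
- *That switching reflects poor tolerability, so the women who did badly disappear.* No reasons for basal switches are given, and women managed by dose, bolus insulin, oral drugs or GLP-1 agonists stay in the set.
- *That the comparator group loses more women.* The asymmetry is in the wording only. The net loss could run the other way.
- *That early losses enrich the primary analysis.* The primary endpoint is restricted to women who completed 22 weeks, so losses before then cannot affect it.
- *That a later switch cannot matter for malformations.* Section 6.5, explaining why gestational diabetes is excluded, describes a time "where the organogenesis is finalized and thereby the risk of malformation significantly reduced". That means reduced risk, not none. The protocol does not date the end of organogenesis, and the argument does not cover perinatal or neonatal death.

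**Conclusion.** The concern holds in a limited form. The protocol fixes one analysis set that selects on a change made after exposure began, applies it to every endpoint, and names no analysis that keeps the switchers. Adjustment within the set cannot correct this.

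The size cannot be read from the protocol. Under the assumed shares and ratios it is about 0.2 to 0.6 points on the primary endpoint at the 2.7% event rate, up to 1.7 points at 8.2%, and nil when switching is equal and equally prognostic. The direction is not known. Every value is below the 3.5-point target difference, and at the observed event rate the effect is small unless switching is both very unequal and strongly prognostic. Maternal endpoints with higher rates could be shifted more in absolute terms.

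The illustration assumes that groups with different switching shares have the same overall risk. If more switching in one group reflects case mix at baseline, part of any difference would be confounding, which the added analysis would still need to adjust for.

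**What to change.** Amend Sections 1, 4.1, 5.1, 13 and 14.4 to add a pre-specified analysis of the primary, maternal and pregnancy-outcome endpoints by basal insulin at conception. All women who switch later, in both groups, stay in their original group. Inclusion criterion 5 already ensures an unchanged product from 4 weeks before to 4 weeks after conception. Report this analysis beside the non-switcher analysis, with the number, timing and available reasons for switching by group.

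Do not repair the asymmetry by putting only the within-comparator switchers back into the existing set. With assumed risks of 2.5% in non-switchers and 5.0% or 7.5% in switchers, and 10% such women retained, the comparator would show 0.9 × 2.5 + 0.1 × 5.0 = 2.75%, or 0.9 × 2.5 + 0.1 × 7.5 = 3.0%, against 2.5% for Levemir. That is a spurious 0.25 to 0.5 points in Levemir's favour.

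Reconcile Section 5.1 (changes after the baseline visit) with Section 13 (changes at any time in pregnancy).

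Cost: protocol wording in five places, SAP text and one more analysis set. Switchers remain in the registry, and product changes are recorded at routine visits and delivery (Sections 8.1.2 and 8.1.3.1), so no data collection is added. The downside is small: later exposure is mixed in the added analysis.
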